Appendix 3. ECOG Performance Status Scores

Status	Eastern Cooperative Oncology Group (ECOG) Performance Status**
0	Fully active, able to carry on all predisease performance without restriction.
1	Restricted in physically strenuous activity but ambulatory and able to carry out work of a light or sedentary nature, eg, light housework, office work.
2	Ambulatory and capable of all self-care, but unable to carry out any work activities. Up and about more than 50% of waking hours.
3	Capable of only limited self-care, confined to bed or chair more than 50% of waking hours.
4	Completely disabled. Cannot carry on any self-care. Totally confined to bed or chair.
5	Dead.

Available at: http://www.ecog.org/general/perf_stat.html. Accessed January 4, 2008.

Appendix 4. Inhibitors and Inducers of CYP3A

Inhibitors and inducers of CYP3A enzymes are defined as follows. A comprehensive list of inhibitors can be found at the following website: http://medicine.iupui.edu/clinpharm/ddis/main-table/. The general categorization into strong, moderate, and weak inhibitors according to the website is displayed below. Refer to Section 6.2.1 on instructions for concomitant use of CYP3A inhibitors and inducers with ibrutinib.

Inhibitors of CYP3A	Inducers of CYP3A
Strong inhibitors:	Carbamazepine
INDINAVIR	Efavirenz
NELFINAVIR	Nevirapine
RITONAVIR	Barbiturates
CLARITHROMYCIN	Glucocorticoids
ITRACONAZOLE	Modafinil
KETOCONAZOLE	Oxcarbarzepine
NEFAZODONE	Phenobarbital
SAQUINAVIR	Phenytoin
SUBOXONE	Pioglitazone
TELITHROMYCIN	Rifabutin
Moderate inhibitors:	Rifampin
Aprepitant	St. John's Wort
Erythromycin	Troglitazone
diltiazem	-
Fluconazole	
grapefruit juice	
Seville orange juice	
Verapamil	
Weak inhibitors:	
Cimetidine	
All other inhibitors:	
Amiodarone	
NOT azithromycin	
Chloramphenicol	
Boceprevir	
Ciprofloxacin	
Delaviridine	
diethyl-dithiocarbamate	
Fluvoxamine	
Gestodene	
Imatinib	
Mibefradil	
Mifepristone	
Norfloxacin	
Norfluoxetine	
star fruit	
Telaprevir	
Troleandomycin	
Voriconazole	

Source: http://medicine.iupui.edu/clinpharm/ddis/main-table/.

Appendix 5. Revised Criteria for Response Assessment of Malignant Lymphoma (Cheson 2014)

The following table provides a summary of response criteria for malignant lymphoma according to Cheson (2014). Please refer to published international guidelines for the most recent and complete details.

Response	Site	PET-CT-Based Response	CT-Based Response
Complete Response	Lymph nodes and	Complete metabolic response	Complete radiologic response (all of the following)
(CR)	extralymphatic sites	Score 1, 2, or 3 ^{a, b} with or without a residual mass on 5PS ^b	Target nodes/nodal masses must regress to ≤1.5 cm in LDi
		It is recognized that in Waldeyer's ring or extranodal sites with high physiologic uptake or with activation within spleen or marrow (eg, with chemotherapy or myeloid colony-stimulating factors), uptake may be greater than normal mediastinum and/or liver. In this circumstance, complete metabolic response may be inferred if uptake at sites of initial involvement is no greater than surrounding normal tissue even if the tissue has high physiologic uptake	No extralymphatic sites of disease
	Non measured lesion	Not applicable	Absent
	Organ enlargement	Not applicable	Regress to normal
	New lesions	None	None
	Bone marrow	No evidence of FDG-avid disease in marrow	Normal by morphology; if determinate, IHC negative
Partial Response	Lymph nodes and	Partial metabolic response	Partial remission (all of the following)
(PR)	extralymphatic sites	Score 4 or 5 ^b with reduced uptake compared with baseline and residual mass(es) of any size	\geq 50% decrease in SPD of up to 6 target measurable nodes and extranodal sites
		At interim, these findings suggest responding disease At end of treatment, these findings indicate	When a lesion is too small to measure on CT, assign 5 mm × 5 mm as the default value
		residual disease	When no longer visible, 0×0 mm For a node >5 mm × 5 mm, but smaller than normal, use actual measurement for calculation
	Nonmeasured lesion	Not applicable	Absent/normal, regressed, but no increase
	Organ enlargement	Not applicable	Spleen must have regressed by >50% in length beyond normal
	New lesions	None	None

Table 6.1:	Criteria for Response	Assessment of Non-Hod	gkin's Lymphoma

Response	Site	PET-CT-Based Response	CT-Based Response
	Bone marrow	Residual uptake higher than uptake in normal marrow but reduced compared with baseline (diffuse uptake compatible with reactive changes from chemotherapy allowed). If there are persistent focal changes in the marrow in the context of a nodal response, consideration should be given to further evaluation with MRI or biopsy or an interval scan	Not applicable
No response		No metabolic response	Stable disease
or stable disease (SD)	Lymph nodes and extralymphatic sites	Score 4 or 5 with no significant change in FDG uptake from baseline at interim or end of treatment	<50% decrease from baseline in SPD of up to 6 dominant, measurable nodes and extranodal sites; no criteria for progressive disease are met
	Non measured	Not applicable	No increase consistent with
	Organ enlargement	Not applicable	No increase consistent with progression
	New lesions	None	None
Drogrossivo	Bone marrow	No change from baseline	Not applicable
disease (PD)	Individual target nodes/nodal masses	Score 4 or 5 with an increase in intensity of uptake from baseline and/or meets criteria below for new EDG-avid foci	Progressive disease requires at least 1 of the following.
	Extranodal lesions	New FDG-avid foci consistent with lymphoma at interim or end-of-treatment assessment	 An individual node/lesion must be abnormal with: LDi >1.5 cm AND Increase by ≥50% from PPD nadir AND An increase in LDi or SDi from nadir: 0.5 cm for lesions ≤2 cm; 1.0 cm for lesions >2 cm In the setting of splenomegaly, the splenic length must increase by >50% of the extent of its prior increase beyond baseline (eg, a 15-cm spleen must increase by at least 2 cm from baseline
	Non measured lesions	None	New of recurrent spienomegaly New or clear progression of preexisting nonmeasured lesions
	New lesions	New FDG-avid foci consistent with lymphoma rather than another etiology (eg, infection, inflammation). If uncertain regarding etiology of new lesions, biopsy or interval scan may be considered	Regrowth of previously resolved lesions A new node >1.5 cm in any axis A new extranodal site >1.0 cm in any axis; if <1.0 cm in any

Response	Site	PET-CT-Based Response	CT-Based Response
			axis, its presence must be unequivocal and must be attributable to lymphoma Assessable disease of any size unequivocally attributable to lymphoma
	Bone marrow	New or recurrent FDG-avid foci	New or recurrent involvement

Abbreviations: 5PS, 5-point scale; CT, computed tomography; FDG, fluorodeoxyglucose; IHC, immunohistochemistry; LDi, longest transverse diameter of a lesion; MRI, magnetic resonance imaging; PET, positron emission tomography; PPD, cross product of the LDi and perpendicular diameter; SDi, shortest axis perpendicular to the LDi; SPD, sum of the product of the perpendicular diameters for multiple lesions.

Footnotes:

- a: A score of 3 in many patients indicates a good prognosis with standard treatment, especially if at the time of an interim scan. However, in trials involving PET where de-escalation is investigated, it may be preferable to consider a score of 3 as inadequate response (to avoid undertreatment). Measured dominant lesions: Up to six of the largest dominant nodes, nodal masses, and extranodal lesions selected to be clearly measurable in two diameters. Nodes should preferably be from disparate regions of the body and should include, where applicable, mediastinal and retroperitoneal areas. Non-nodal lesions include those in solid organs (eg, liver, spleen, kidneys, lungs), GI involvement, cutaneous lesions, or those noted on palpation. Nonmeasured lesions: Any disease not selected as measured, dominant disease and truly assessable disease should be considered not measured. These sites include any nodes, nodal masses, and extranodal sites not selected as dominant or measurable or that do not meet the requirements for measurability but are still considered abnormal, as well as truly assessable disease, which is any site of suspected disease that would be difficult to follow quantitatively with measurement, including pleural effusions, ascites, bone lesions, leptomeningeal disease, abdominal masses, and other lesions that cannot be confirmed and followed by imaging. In Waldever's ring or in extranodal sites (eg, GI tract, liver, bone marrow), FDG uptake may be greater than in the mediastinum with complete metabolic response, but should be no higher than surrounding normal physiologic uptake (eg, with marrow activation as a result of chemotherapy or myeloid growth factors).
- b: PET 5PS: 1, no uptake above background; 2, uptake ≤ mediastinum; 3, uptake > mediastinum but ≤ liver; 4, uptake moderately > liver; 5, uptake markedly higher than liver and/or new lesions; X, new areas of uptake unlikely to be related to lymphoma.

Appendix 6. New York Heart Association (NYHA) Functional Classification

Class	Functional Capacity: How a patient with cardiac disease feels during physical activity
Ι	Patients with cardiac disease but resulting in no limitation of physical activity. Ordinary physical activity does not cause undue fatigue, palpitation, dyspnea or anginal pain.
Π	Patients with cardiac disease resulting in slight limitation of physical activity. They are comfortable at rest. Ordinary physical activity results in fatigue, palpitation, dyspnea or anginal pain.
III	Patients with cardiac disease resulting in marked limitation of physical activity. They are comfortable at rest. Less than ordinary activity causes fatigue, palpitation, dyspnea or anginal pain.
IV	Patients with cardiac disease resulting in inability to carry on any physical activity without discomfort. Symptoms of heart failure or the anginal syndrome may be present even at rest. If any physical activity is undertaken, discomfort increases.

Reference:

The Criteria Committee of the New York Heart Association. Nomenclature and Criteria for Diagnosis of Diseases of the Heart and Great Vessels. 9th ed. Boston, Mass: Little, Brown & Co; 1994:253-256.

Appendix 7. Contraception Requirements for MEDI4736

- Females of childbearing potential who are sexually active with a nonsterilized male partner must use 2 methods of effective contraception from screening, and must agree to continue using such precautions for 90 days after the final dose of investigational product; cessation of birth control after this point should be discussed with a responsible physician. Periodic abstinence, the rhythm method, and the withdrawal method are not acceptable methods of birth control.
- Females of childbearing potential are defined as those who are not surgically sterile (ie, bilateral tubal ligation, bilateral oophorectomy, or complete hysterectomy) or postmenopausal (defined as ≥60 years old and no menses for ≥1 year without an alternative medical cause).
- Subjects must use 2 acceptable methods of effective contraception as described in the table below.
- Nonsterilized males who are sexually active with a female partner of childbearing potential must use 2 acceptable methods of effective contraception (see Table below) from Day 1 and for 90 days after receipt of the final dose of investigational product.

Barrier Methods	Intrauterine Device Methods	Hormonal Methods
Male condom plus spermicide	Copper T	Implants
Cap plus spermicide	Progesterone T	Hormone shot or injection
Diaphragm plus spermicide	Levonorgestrel-releasing intrauterine system (eg, Mirena [®])	Combined pill
		Minipill
		Patch

Effective methods of contraception (two methods must be used)

Ig	Immunoglobulin
IHC	immunohistochemistry
IND	Investigational New Drug
INR	international normalized ratio
IV	Intravenous
LLN	low limit of normal
MAD	maximum administered dose
MedDRA	Medical Dictionary for Regulatory Activities
MEDI4736	durvalumab
MRD	minimal residual disease
MRI	magnetic resonance imaging

MTD	maximum tolerated dose
NHL	non-Hodgkin's lymphoma
Non-GCB	Non-Germinal Center B-cell like
ORR	objective response rate
OS	overall survival
PD	progressive disease
PFS	Progression-free survival
PK	pharmacokinetics
PO	per os (oral)
PR	partial remission (response)
RP2D	recommended phase 2 dose
PT	prothrombin time
QTc	corrected QT interval
SAE(s)	serious adverse event(s)
SAP	statistical analysis plan
SD	stable disease
SI	standard international units
SOC	system organ class
ULN	upper limit of normal

1. INTRODUCTION

This statistical analysis plan (SAP) lays out key elements including definitions and statistical methods for analysis of data in evaluation of efficacy and safety for the PCYC-1136-CA study. Analyses of pharmacokinetics data and biomarkers will be addressed in separate documents.

1.1. Study Design

This is a Phase 1b/2, open-label multi-center study to assess the safety and efficacy of ibrutinib in combination with MEDI4736 in subjects with relapsed or refractory lymphomas. A 6+3 de-escalation design will be employed in Phase 1b to assess doses of ibrutinib in combination with MEDI4736 to determine the recommended Phase 2 dose (RP2D) for this study.

Phase 1b:

In the safety portion of the study, a starting dose of 560 mg of ibrutinib and 10 mg/kg of MEDI4736 will be explored in Cohort 1 and will follow a 6+3 dose de-escalation design including a sentinel subject with at least a 3-day observation period in each Phase 1b dosing cohort prior to dosing additional subjects to monitor for any unexpected acute or overlapping toxicities.

Subjects with one of the following two tumor types will be eligible for enrollment in Phase 1b:

- Follicular lymphoma (FL) (grade 1, 2, or 3A)
- Diffuse large B cell lymphoma (DLBCL)

In cohort 1, ibrutinib will be administered orally (PO) daily in 6 subjects at a dose of 560 mg in combination with MEDI4736 at a dose of 10 mg/kg intravenously (IV) every 2 weeks in 28-day cycles for 12 months or until unacceptable toxicity or disease progression occurs.

As a lead-in to the first cycle, ibrutinib will be given for 7 days prior to starting MEDI4736 in order to obtain single agent PK and biomarker samples that will be compared to combination therapy. Per the protocol, the 7-day lead-in period of ibrutinib is not part of the dose-limiting toxicity (DLT) evaluation period. The DLT assessment will occur from Day 1 of Cycle 1 of the combination therapy until the laboratory evaluations on Day 1 of Cycle 2 (28 days). If the subject incidence of DLTs from Day 1 of Cycle 1 of combination therapy to the laboratory evaluations on Day 1 of Cycle 2 is <33.3% (ie, ≤ 1 of 6 or ≤ 2 of 9 subjects with a DLT), this dose level will be considered safe to proceed to Phase 2, and will be defined as the RP2D. If 2 subjects within the initial cohort of 6 subjects experience a DLT, an additional 3 subjects will be enrolled at the same dose level. If 3 or more of 6-9 subjects experience a DLT, dose de-escalation will occur. A similar 6+3 cohort design will be utilized in the de-escalation cohorts. De-escalation cohorts -1A and -1B will be opened simultaneously to determine which dosing schedule is most appropriate for the Phase 2 portion of the study (for cohort definitions, see

section 4.2: Study Treatment). Determination will be based on the safety profile of the 2 treatment regimens. If necessary, the dose de-escalation cohort -2 will be enrolled thereafter.

The Phase 1b DLT observation period will occur from Day 1 of Cycle 1 of ibrutinib in combination with MEDI4736 treatment until the laboratory evaluations on Day 1 of Cycle 2 which will occur before the MEDI4736 infusion on Day 1 of Cycle 2. A DLT is an AE at least possibly related to study drug(s) defined as:

Any Grade 3 or higher non-hematologic AE (with additional clarifications below)

- Grade 3 or higher nausea, vomiting, or diarrhea (non-colitis-related) that is uncontrolled by maximal supportive care and persists for >7 days would be considered a DLT
- Grade 3 fatigue that persists for >7 days would be considered a DLT
- Any Grade 3-immune related adverse event (irAE) that does not downgrade to Grade ≤ 2 within 3 days after onset of the event despite maximal supportive care including systemic corticosteroids, or does not downgrade to Grade ≤ 1 or baseline within 14 days would be considered a DLT
- Any Grade ≥ 2 pneumonitis that does not resolve to Grade ≤ 1 within 3 days of the initiation of maximal supportive care would be considered a DLT.
- The DLT definition excludes the following conditions:
 - Grade 3 endocrinopathy that is managed with or without systemic corticosteroid therapy and/or hormone replacement therapy and the subject is asymptomatic
 - Grade 3 inflammatory reaction attributed to a local antitumor response (eg, inflammatory reaction at sites of metastatic disease, lymph nodes, etc.)
 - Vitiligo or alopecia of any AE grade would not be considered a DLT

Clinically relevant hematologic AE such as:

- Grade 3 or 4 neutropenia ($ANC < 1,000/mm^3$) lasting >7 days
- Febrile neutropenia (Grade 3 or 4 neutropenia with fever $\geq 38.3^\circ C$)
- Grade 3 or 4 thrombocytopenia ($< 25,000/mm^3$) lasting >7 days or requiring transfusion or associated with Grade ≥ 2 bleeding
- Any other Grade 4 hematologic AE, except lymphopenia

During the Phase 1b DLT observation period of ibrutinib in combination with MEDI4736, subjects will be replaced for any of the following reasons:

- Missed ≥ 5 consecutive doses of ibrutinib or missed 7 total doses (not due to DLT)
- Missed dose of MEDI4736 or received the MEDI4736 dose outside of the protocol-allowed window (± 2 days) (not due to DLT)
- Study drug discontinuation for any reason other than DLT

After the RP2D of ibrutinib in combination with MEDI4736 is defined, enrollment in Phase 2 will commence.

Phase 2:

Two tumor types will be enrolled in separate cohorts as part of this protocol:

- Follicular lymphoma (FL) (grade 1, 2, or 3A)
- Diffuse large B cell lymphoma (DLBCL)

For FL: n = 39

The FL cohort will enroll 39 response-evaluable subjects. An interim analysis will be performed after 19 subjects are evaluable for tumor response after completing at least 1 response assessment. If only 6 or fewer responders ($\leq 6/19$) are observed, the Sponsor may consider discontinuation of this cohort; however, assessment of biomarkers (that may aid in prospective enrichment of responders) or tumor measurements (showing clinically relevant tumor reductions, ie, 40%, that fit the criteria for SD) may support continued enrollment.

For DLBCL: n = 34

Subjects with germinal center B-cell (GCB) and non-GCB subtypes will be enrolled at a 1:1 ratio approximately. The DLBCL cohort will enroll 34 response-evaluable subjects. An interim analysis will be performed after 9 subjects are evaluable for tumor response after completing at least 1 response assessment. If only 1 or fewer responder ($\leq 1/9$) is observed, the Sponsor may consider discontinuation of this cohort; however, assessment of biomarkers (that may aid in prospective enrichment of responders) or tumor measurements (showing clinically relevant tumor reductions, ie, 40%, that fit the criteria for SD) may support continued enrollment.

In the DLBCL cohort, additional prospectively identified non-GCB subjects may be enrolled if a 22% ORR (2/9) is not achieved at the interim analysis in the unselected DLBCL population so that at least a total of 16 subjects with the non-GCB subtype are evaluated.

Note: The Phase 2 subjects include all of those response-evaluable subjects treated at R2PD in Phase 1b but with tumor type as defined for Phase 2.

During the Phase 2 portion of the study, if a subject discontinues study drug prior to the first tumor response assessment for reasons other than progressive disease, the subject may be replaced.

The primary analysis will occur at least 12 months after the last FL subject is enrolled and at least 9 months after the last DLBCL subject is enrolled.

Dosing of ibrutinib in combination with MEDI4736 will continue for a total of 12 cycles of therapy if the subject is deriving clinical benefit (CR, PR, or SD) and the subject is not experiencing unacceptable toxicity. After 12 cycles, dosing of ibrutinib alone will continue as

long as clinical benefit is seen without safety concerns or disease progression. Response evaluations will occur on Day 1 of Cycle 3 and then after every 3rd cycle through the 1st year and after every 6th cycle thereafter. Assessment will follow the Revised Criteria for Response Assessment of Malignant Lymphoma (Cheson 2014) using CT criteria.

In order to accommodate the potential for immune flare (pseudoprogression), treatment with MEDI4736 and ibrutinib may continue between the initial assessment of suspected progression and confirmation of progression. Subjects with presumed progressive disease (PD) who, in the Investigator's opinion, continue to receive clinical benefit from their treatment may continue to receive MEDI4736 and ibrutinib as dictated in the protocol after consultation with the Sponsor and at the Investigator's discretion. In the absence of clinically significant deterioration, a CT scan or biopsy may be performed at least 4 weeks later to confirm PD. If PD is confirmed at the later time point, PD should be assigned to the prior time point at which PD criteria were also met. MEDI4736 and ibrutinib should be discontinued if there is confirmed PD per Revised Criteria for Response Assessment of Malignant Lymphoma (Cheson 2014) or other clinical data suggest clear evidence of progression.

Subjects are required to undergo a pre-treatment tumor biopsy for all phases of this study; a post-progression biopsy is recommended but will be optional.

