Data from Study PCYC-04753 demonstrate that although ibrutinib is rapidly eliminated from the plasma after oral administration, once daily dosing with ibrutinib is adequate to sustain maximal pharmacodynamic activity for 24 hours postdose at dose levels \geq 2.5 mg/kg. In Study PCYC-04753, the BTK occupancies for the 2.5 mg/kg/day to 12.5 mg/kg/day cohorts and for the 560 mg continuous dosing cohort, were all above 90% at either 4 or 24 hours after drug administration.

Sixteen subjects enrolled in the dose-escalation phase of Study PCYC-04753 had a diagnosis of FL (Fowler 2012). Eleven subjects received ibrutinib at doses that achieved full BTK occupancy (ie, 2.5 mg/kg or higher). The median time on ibrutinib was 7 months (0 to 29 months) and time to response was 4.6 months. Overall, the response rate was 55% (3 CRs, 3 PRs; 95% confidence interval [CI]=[23%, 83%])(Fowler 2012) and the responses were durable (median response duration: 12.3 months) (Fowler 2012). Three patients had chemorefractory disease, and 2 of these patients responded (1 CR, 1 PR). The median PFS at study completion for subjects with FL was 13.4 months (Study PCYC-04753 CSR).

Ibrutinib has also demonstrated single agent activity in the treatment of relapsed or refractory de novo DLBCL in Study PCYC-1106-CA. Study PCYC-1106-CA is an ongoing Phase 2, open-label, nonrandomized, multicenter study in patients with relapsed or refractory de novo DLBCL receiving 560 mg/day of ibrutinib. Data are currently available on 70 patients from this trial who have relapsed or refractory disease with 29 ABC subtype, 20 GCB subtype, 16 Type 3 subtype and 5 subjects subtype unknown. The ORR in these 70 patients was 25% (17/70) with 9% of patients achieving a complete response (CR) and 16% of patients achieving a partial response (PR). Patients with ABC subtype appeared to be the most sensitive with an ORR of 41% (12/29) with 17% CR and 24% PR (de Vos 2013).

For the most comprehensive nonclinical and clinical information regarding ibrutinib background, safety, efficacy, and in vitro and in vivo preclinical activity and toxicology of ibrutinib, refer to the latest version of the ibrutinib Investigator's Brochure (IB).

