Two tumor types will be enrolled in separate cohorts as part of this protocol:

- Follicular lymphoma (FL) (grade 1, 2, or 3A)
- Diffuse large B-cell lymphoma (DLBCL)

FL: n = 39

The FL cohort will be enrolled prospectively without further subclassification. An interim analysis will be performed after 19 subjects are evaluable for tumor response after completing at least 2 response assessments (\geq Cycle 6 Day 1). If only 6 or fewer responders (\leq 6/19) are observed, the Sponsor may consider discontinuation of this cohort; however, assessment of biomarkers (that may aid in prospective enrichment of responders) or tumor measurements (showing clinically relevant tumor reductions, ie, 40%, that fit the criteria for SD) may support continued enrollment (see Section 12.11). If a subject discontinues prior to the first tumor response assessment for reasons other than progressive disease, the subject will be replaced (see Section 5.4).

DLBCL: n = 34

Subjects with GCB and non-GCB subtypes will be enrolled at a 1:1 ratio approximately. An interim analysis will be performed after 9 subjects are evaluable for tumor response after completing at least 2 response assessments (\geq Cycle 6 Day 1). If only 1 or fewer responder (\leq 1/9) is observed, the Sponsor may consider discontinuation of this cohort; however, assessment of biomarkers (that may aid in prospective enrichment of responders) or tumor measurements (showing clinically relevant tumor reductions, ie, 40%, that fit the criteria for SD) may support continued enrollment (see Section 12.11). If a subject discontinues prior to the first tumor response assessment for reasons other than progressive disease, the subject will be replaced (see Section 5.4).

In the DLBCL cohort, additional prospectively identified non-GCB subjects may be enrolled if a 22% ORR (2/9) is not achieved at the interim analysis in the unselected DLBCL population so that at least a total of 16 subjects with the non-GCB subtype are evaluated.

Note: The Phase 2 subjects include all of those subjects treated at R2PD in Phase 1b that have the tumor type as defined for Phase 2.

The primary analysis will occur at least 12 months after the last FL subject is enrolled and at least 9 months after the last DLBCL subject is enrolled.

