1.3. Statistical Hypotheses

There is no hypothesis testing for Phase 1b. The primary objective of Phase 2 is to evaluate overall response rate (ORR) for the combination therapy at RP2D. Hypothesis testing will be conducted to address this objective as follows:

Null hypothesis (H_0): $P \leq x\%$; where P denotes overall response rate.

Alternative hypothesis (H_a): $P > y\%$; where P denotes overall response rate.

For FL cohort, a true response rate of 30% (H_0) versus 50% (H_a) will be tested. For DLBCL cohort, a true response rate of 15% (H_0) versus 35% (H_a) will be tested.

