1.4. Sample Size Determination**Phase 1b:**

6-36 subjects for DLT assessment (6-9 subjects in up to 4 dose de-escalation cohorts, regardless of tumor type).

Phase 2:

Approximately 73 response-evaluable subjects (including those subjects treated at the RP2D in Phase 1b but with tumor type as defined for Phase 2).

For FL:

A maximum of 39 response-evaluable subjects (including those subjects treated at the RP2D in Phase 1b and with tumor type of FL) will be enrolled. An interim analysis will be performed after 19 subjects are evaluable for tumor response after completing at least 1 response assessment. If only 6 or fewer responders ($\leq 6/19$) are observed, the Sponsor may consider discontinuation of this cohort.

The null hypothesis that the true ORR is 30% will be tested against a one-sided alternative that the ORR is 50%. The null hypothesis will be rejected if 17 or more responses are observed in the 39 subjects. This design yields a 1-sided type I error rate of 0.05 and power of 80% when the true ORR is 50%. This statistical design including number of subjects and number of responders follows the statistical framework of Simon's minimax two-stage design (Simon, 1989). Enrollment will continue while the interim analysis is performed.

For DLBCL:

A maximum of 34 response-evaluable subjects with GCB and non-GCB (inclusive of subjects treated at the RP2D in Phase 1b in the unselected DLBCL population) will be enrolled at a 1:1 ratio approximately.

An interim analysis will be performed after 9 subjects are evaluable for tumor response after completing at least 1 response assessment. If only 1 or fewer responder ($\leq 1/9$) is observed, the Sponsor may consider discontinuation of this cohort.

The null hypothesis that the true ORR is 15% will be tested against a one-sided alternative that the ORR is 35%. The null hypothesis will be rejected if 9 or more responses are observed in the 34 subjects. This design yields a 1-sided type I error rate of 0.05 and power of 80% when the true ORR is 35%. This statistical design including number of subjects and number of responders follows the statistical framework of Simon's optimal two-stage design (Simon 1989). Enrollment will continue while the interim analysis is performed.

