2.1. Analysis Sets

Response-evaluable Population

The Response-evaluable Population is defined as all enrolled subjects who received at least one dose of study treatment (ibrutinib or MEDI4736) and provided at least one post-baseline response assessment. This population includes all the qualified subjects from both Phase 1b and Phase 2. The Response-evaluable Population will be used as the primary population for analyses based on overall response rate. In the analysis, subjects who had clinical progression per investigator will be included in the response-evaluable population.

Safety Population (Treated Population)

Safety population (Treated Population) includes all subjects who were enrolled in the study and received at least 1 dose of study treatment (ibrutinib or MEDI4736). The safety population will

be used to summarize the safety (including dosing) data and for the analysis of PFS, OS and ORR sensitivity analysis.

DLT Evaluable Population for Phase 1b

DLT evaluable population includes Phase 1b subjects who received study treatment and did not meet the criteria for subject replacement during the DLT observation period.

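### Non-GCB subjects added after a failed DLBCL interim enter the pooled DLBCL ORR and the 9/34 count by default, so a change in subtype mix can raise the tested result

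*SAP*

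**What the plan says.** **The test.** SAP Section 1.3: "For DLBCL cohort, a true response rate of 15% (H_0) versus 35% (H_a) will be tested". SAP Section 1.4: "The null hypothesis will be rejected if 9 or more responses are observed in the 34 subjects". The same section describes a Simon optimal two-stage design with an interim at 9 subjects and a futility boundary of 1 or fewer responders. The cohort has a maximum of 34 response-evaluable subjects, GCB and non-GCB in a ratio of about 1:1.

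**The provision.** SAP Section 1.1 and Protocol Section 3.1.2 share one rule: "additional prospectively identified non-GCB subjects may be enrolled if a 22% ORR (2/9) is not achieved at the interim analysis in the unselected DLBCL population". Both documents place it within the DLBCL cohort and give its purpose as a minimum count: "so that at least a total of 16 subjects with the non-GCB subtype are evaluated". This is optional. The sponsor may instead stop the cohort, or continue it on biomarker or tumor-measurement grounds. No upper limit on the added subjects and no new total is given.

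**The analysis.** Protocol Section 10.6.2.1 defines the primary analysis as ORR in the response-evaluable population of each of the two tumor cohorts, and SAP Table 1 uses the same population. SAP Section 2.1 defines that population as every enrolled subject with at least one dose and one post-baseline response assessment, and adds "This population includes all the qualified subjects from both Phase 1b and Phase 2". ORR with a 95% CI by subtype is prespecified (Protocol Section 10.6.2.4, SAP Section 2.2 and Table 1), with no hypothesis or decision rule.

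**The concern.** The provision acts only after the unselected cohort has missed 2/9, and from then on selects subjects by subtype. Nothing in the analysis sections separates those subjects from the cohort they are added to. Followed as written, the plan computes one DLBCL ORR on a mix that was changed because of the interim result, and compares it with a null and a count set for a cohort enrolled about 1:1.

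If the subtypes respond differently, the pooled ORR moves with the mix. A cohort that failed its first stage could then cross 9/34, and the result would no longer describe unselected DLBCL. The trigger is not rare: at a true ORR of 15%, 1 or fewer of 9 occurs with probability 0.60.

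**Working it through.** **1. The plan's own figures.** Let B(n, p) be a binomial count. Under the binding two-stage rule,

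P(reject) = Σ over i = 2..9 of P(B(9, p) = i) × P(B(25, p) ≥ 9 − i).

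This gives 0.0474 at p = 0.15 and 0.811 at p = 0.35, so the stated 0.05 and 80% reproduce. If the futility rule is ignored and enrolment simply continues, P(B(34, p) ≥ 9) is 0.0587 and 0.891.

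**2. How far the mix can move.** Assume five non-GCB and four GCB subjects in the first nine, with only non-GCB added afterwards.
- Planned: 17/34 = 50% non-GCB.
- Stated minimum of 16 non-GCB: 16/20 = 80%.
- Filled to 34: 30/34 = 88%.

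**3. Why a subtype difference is plausible.** Protocol Section 1.3 reports ibrutinib alone at 12/29 (41%) in ABC and 17/70 overall, so 5/41 (12%) outside ABC by subtraction. ABC is not the same group as non-GCB, and rates for the 20 GCB and 16 Type 3 subjects are not given. Count Type 3 as non-GCB (29 + 16 = 45) and leave out the 5 of unknown subtype:
- All five other responders in Type 3 (17/45 and 0/20): the expected ORR goes from 18.9% at 1:1 to 30.2% at 16:4, a shift of about 11 points.
- All five in GCB (12/45 and 5/20): it goes from 25.8% to 26.3%, a shift of 0.5 points.

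The direction is plausible, but the size is open.

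**4. Effect on the 9/34 rule.** Let pN and pG be the true non-GCB and GCB rates, with (pN + pG)/2 = 15%, so that the 1:1 mix sits on the null. Stage 1 is X = B(5, pN) + B(4, pG).
- If X ≥ 2, the remaining 25 are M = B(12, pN) + B(13, pG).
- If X ≤ 1 and enrolment is restricted, the remaining 25 are Y = B(25, pN).

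P(reject) = Σ over i ≥ 2 of P(X = i) P(M ≥ 9 − i) + Σ over i ≤ 1 of P(X = i) P(Y ≥ 9 − i).

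For continued 1:1 enrolment, M replaces Y. Example at 23%/7%: the interim fails with probability 0.566; passing it and then rejecting has probability 0.0456; rejection after failure is 0.163 if enriched and 0.014 if 1:1 continues. The totals are 0.0456 + 0.566 × 0.163 = 0.138 and 0.0456 + 0.566 × 0.014 = 0.054.

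| non-GCB / GCB rate | Interim fails | Reject after failure: enriched / 1:1 | Total, enriched to 34 | Total, 1:1 continued | Total, enriched to 20, cut-off 7 |
|---|---|---|---|---|---|
| 15% / 15% | 59.9% | 1.9% / 1.9% | 5.9% | 5.9% | 4.8% |
| 20% / 10% | 57.9% | 8.6% / 1.7% | 9.7% | 5.7% | 5.2% |
| 23% / 7% | 56.6% | 16.3% / 1.4% | 13.8% | 5.4% | 5.5% |
| 25% / 5% | 55.6% | 23.0% / 1.3% | 17.2% | 5.1% | 5.8% |
| 30% / 0% | 52.8% | 43.6% / 0.7% | 26.7% | 4.0% | 6.8% |

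In the last column, 9/34 still applies after a passed interim. After a failed one, 11 non-GCB subjects are added and the cut-off of 7 is assumed, because the plan states none for about 20 subjects. It is the smallest with one-sided error at or below 0.05: P(B(20, 0.15) ≥ 7) = 0.022, and for 6 it is 0.067.

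**5. Sensitivity to the first-stage split.** At 30%/0% filled to 34, the total is 31% with four non-GCB and five GCB subjects at the interim, and 19% with seven and two.

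**The case against.** **Pooling is not stated.** Neither document says in terms that the added subjects are pooled. The SAP 2.1 sentence quoted above concerns combining Phase 1b with Phase 2. The added subjects could be read as lying outside a 34-subject test enrolled about 1:1. This stands to the extent that pooling is a default, not an explicit plan. But the provision places them in the DLBCL cohort, the primary analysis takes every response-evaluable subject in that cohort, and nothing excludes them.

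**The large figures need the cohort filled to 34.** This stands. A 30:4 mix departs from about 1:1, and the stated aim is only at least 16 non-GCB, where inflation is small. With no maximum given, filling to 34 is not ruled out.

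**Safeguards exist.** The restriction is optional, and the prespecified subtype ORRs would show a mix effect beside the pooled figure. Both are true, but neither decides what counts toward 9/34.

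**Two stronger inferences are not supported.**
- A reader might infer that the plan would be adding subjects who are easier to treat. Protocol Sections 1.1 and following describe ABC disease as having an inferior prognosis and non-GCB disease as doing poorly on existing options. The documents do not derive the 15%, so they do not show that a non-GCB null should be higher.
- A reader might put the ibrutinib-alone rates into the enriched mix, obtain about 35% at 16:4, and conclude that the trial could succeed with no contribution from MEDI4736. But 17/70 (24%) on ibrutinib alone already lies above the 15% null, and at those rates the planned 1:1 mix (26.8%) crosses 9/34 about 59% of the time without any enrichment. That illustration mostly reflects where the null sits, and a higher non-GCB ORR would be real activity of the regimen in that subtype.

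**Conclusion.** The concern holds, with moderate confidence. After a missed interim, the plan permits selection by subtype and, by default, counts the selected subjects in a test attached to an unselected cohort enrolled about 1:1.

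The bias is conditional. It requires that the option is used, that the subtypes differ, and, for the larger figures, that the cohort is filled to 34. Under the 5:4 first stage with the 1:1 ORR held at 15%, the chance of crossing 9/34 is then 5.9% with no subtype difference, about 10% at 20%/10%, 14% at 23%/7% and 27% at the extreme split of 30%/0%. The comparison with continued 1:1 enrolment is 4.0% to 5.9%. These are scenario values, not the trial's expected error rate.

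At the stated minimum the inflation is small, about 5% to 7% with the assumed cut-off. The defect there is that no rule exists. The calculation also takes exactly nine subjects as enrolled when the restriction begins, in line with the enrolment hold in SAP Section 5. More 1:1 subjects enrolled by then would dilute the effect.

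**What to change.** In SAP Sections 1.1 and 2.1 and Table 1, and in Protocol Section 10.4.2, state that if enrolment is restricted to non-GCB subjects after the interim:

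1. Subjects enrolled under the provision are excluded from the primary pooled DLBCL ORR and from the 9/34 count.
2. The unselected DLBCL ORR with its 95% CI is reported on subjects enrolled before the restriction, and no rejection of the 15% null is claimed from the enriched set.
3. The added subjects are reported in the existing non-GCB subgroup ORR with 95% CI, labelled descriptive.

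The descriptive label fits the numbers. With 16 non-GCB subjects tested alone against 15%, the smallest rule with one-sided error at or below 0.05 is 6/16, with error 0.024 and power of only 0.51 at a true ORR of 35%.

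The cost is wording only, and the option to enrol more non-GCB subjects is kept. What is given up is a late positive claim for unselected DLBCL once enrolment has been restricted.
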